**List of Abbreviations**

CGRP	Calcitonin Gene-Related Peptide
CFR	Code of Federal Regulations
CRF	Case Report Form
CTCAE	Common Terminology Criteria for Adverse Events
DLQI	Dermatology Quality of Life Index
ELISA	Enzyme-linked Immunosorbent Assay
FDA	Food and Drug Administration
GABA	Gamma -Aminobutyric Acid
GCP	Good Clinical Practice
ICH	International Conference on Harmonization
IDS	Investigational Drug Services Pharmacy
IRB	Institutional Review Board
H&E	Hematoxylin and Eosin Stain
LPP	Lichen Planopilaris
LPPAI	Lichen Planopilaris Activity Index
PSA	Primary Scarring Alopecia
SF-36	Short Form (36) Health Survey
UPIRTSO	Unanticipated Problems Involving Risk to Subjects or Others
VAS	Visual Analog Scale

CONFIDENTIAL

This material is the property of the University of Minnesota. Do not disclose or use except as authorized in writing by the study sponsor

## Study Summary

Title	Role of Neurogenic Inflammation and Topical 6% Gabapentin Therapy in Symptomatic Scarring Alopecia
Short Title	Scarring alopecia – Gabapentin study
Methodology	Cohort study
Study Duration	16 weeks for each subject
Study Center(s)	Single-center
Objectives	To determine the role of neurogenic inflammation in scarring alopecia and to assess the safety and efficacy of topical gabapentin in the management of symptomatic scarring alopecia.
Number of Subjects	10 (ten)
Diagnosis and Main Inclusion Criteria	Biopsy-proven scarring alopecia; Men and women greater than 18 years of age. Their scarring alopecia should be symptomatic with symptoms including burning, tingling, itch, pain in addition to hair loss. The subject should have no history of use of neuromodulatory agents two months prior to study enrollment.
Study Product, Dose, Route, Regimen	Gabapentin 6% solution The maximum daily dose of topical gabapentin will be 2 ml with the estimation that no more than one-third of a subject's scalp is affected. The drug will be administered topically by the subject to symptomatic areas of intact skin two times daily for 12 weeks. Based on its half-life of 8 hours when taken orally, gabapentin will be administered two times a day and the dose will not exceed the amount of topical agent used on average to treat the entire scalp in everyday clinical practice (1 mL twice daily, 60 mL per month).
Duration of administration	The drug will be topically applied by the subject two times daily for 12 weeks.
Reference therapy	This is a pilot study and there is no reference therapy against which topical 6% gabapentin will be compared.
Statistical Methodology	An intent-to-treat analysis will be performed in all subjects with symptoms comparing the last visit to baseline.

# 1 Introduction

This document is a protocol for a human research study. This study is to be conducted according to US and international standards of Good Clinical Practice (FDA Title 21 part 312 and International Conference on Harmonization guidelines), applicable government regulations and Institutional research policies and procedures.

## 1.1 Background

Primary scarring alopecias (PSAs) are poorly understood dermatologic disorders that result in permanent hair loss (1). PSAs are classified based on the type of inflammatory infiltrate recognized histologically on biopsy: lymphocytic, neutrophilic, or mixed. As painful hair loss disorders, scarring alopecias have yet to be studied in a manner that explores the disease burden on the individual and how to more effectively manage debilitating symptoms. Most of the scarring alopecias involve a painful course, with individuals reporting scalp pain, burning, itching, or tingling/crawling sensations that can ultimately impact physical and psychological health (1). It is well-documented that individuals with chronic pain are more susceptible to depression and other mood disorders (2). Thus, a better understanding of the pain process in scarring alopecia would benefit patients and health care providers tremendously as scientists research to discover the origin and pathogenesis of these inflammatory and irreversible conditions.

CGRP (calcitonin gene-related peptide) has been proposed to play a role in pain transmission and inflammation (3, 4). While originally found to be elevated in migraines, two patients with lichen planopilaris (LPP) at the University of Minnesota were found to have elevated amounts of CGRP via immunohistochemical staining and confocal microscopic examination of scalp biopsy specimens. Seven patients, three with frontal fibrosing alopecia and four with LPP, were also found to have decreased expression of epidermal nerves as well as CGRP expression. This suggests that neurogenic inflammation may contribute to the disease state of scarring alopecia. Investigating this relationship between CGRP and scalp symptoms such as pain in the setting of scarring alopecia may lead to a long awaited breakthrough in disease pathogenesis and management. Agents that reduce the release of neuropeptides, such as gabapentin, may serve as potential treatment in scarring alopecia. Recent data from pilot experiments at the University of Minnesota using normal human tissue stimulated by gabapentin reflected a reduction in CGRP compared to levels of CGRP in control unstimulated tissue, indicating that CGRP may realistically be an appropriate therapeutic target in scarring alopecia.

## 1.2 Investigational Agent

Gabapentin is a GABA analogue originally introduced in 1994 for the treatment of epilepsy by Warner-Lambert (today Pfizer). It is currently widely used to relieve pain, especially neuropathic pain syndromes associated with diabetic neuropathy, vulvodynia, postherpetic neuralgia and other allodynia (5, 6). While gabapentin's mechanism of action is not completely understood, it is thought to work through its effects on voltage-gated calcium ion channels in the central nervous system once it crosses the blood-brain barrier (7). Its neuromodulatory effects also impact the peripheral nervous system.

CONFIDENTIAL

This material is the property of the University of Minnesota. Do not disclose or use except as authorized in writing by the study sponsor

### **1.3 Preclinical Data**

Currently, the management of symptomatic scarring alopecia includes intralesional triamcinolone injections alone or with topical steroid solutions, minoxidil, oral antibiotics, hydroxychloroquine or immunosuppressive medications such as prednisone. Since the cause of scarring alopecia is unknown, the various modes of treatment have focused on targeting the inflammation associated with the disease process that is reflected histologically. No one treatment has been found successful in all conditions nor is there a cure. Individuals with end-stage, non-symptomatic disease may be candidates for hair transplantation.

### **1.4 Clinical Data to Date**

There has been no study of topical neurogenic agents, such as gabapentin, to treat scarring alopecia. However topical gabapentin has been safely used in other conditions associated with chronic pain, burning, irritation, itch, or tingling, such as vulvodynia (5).

Interestingly, gabapentin has been shown to be effective against migraine headaches, a condition associated with high levels of CGRP (6). Gabapentin has also been shown to be effective in managing neuropathic pain. This evidence suggests that gabapentin could be effective in the treatment of scarring alopecia, especially if increased CGRP is contributing to symptomatology.

This study will serve as a pilot study to determine the efficacy and safety of topical gabapentin in the treatment of symptomatic scarring alopecia. In this study, 10 subjects with symptomatic lymphocytic-type scarring alopecia will be recruited and treated with topical gabapentin. Disease burden will be evaluated before and after 12 weeks of treatment through reporting of subjective symptomatology via surveys/questionnaire, neurometer study, clinical assessment, and biopsies measuring levels of CGRP before and after treatment.

### **1.5 Dose Rationale and Risk/Benefits**

The maximum daily dose of topical gabapentin will be 2 mL daily. The drug will be administered topically by the subject to symptomatic affected areas of intact skin two times daily for 12 weeks. Subjects will be seen in follow up on Week 8 and Week 12 (Visits 4 and 5).

Gabapentin will be compounded into a 6% solution based on a preparation method described by Boardman et al. (5) and approved by Investigational Drug Services (IDS) Pharmacy, University of Minnesota. IDS will prepare and dispense the drug.

From published data in which gabapentin was used in a cohort group with nerve-related symptoms from localized or generalized vulvodynia, the most frequently reported adverse effect was irritation at the site of application, which led to termination of use (8%). Common adverse effects of oral gabapentin, including dizziness, somnolence, and peripheral edema, were not reported by any of the patients studied with vulvodynia. In this pilot study for scarring alopecia, the maximum daily dose will not exceed 2 mL of topical gabapentin 6% solution to affected scalp surface.

CONFIDENTIAL

This material is the property of the University of Minnesota. Do not disclose or use except as authorized in writing by the study sponsor

Based on its half-life of 8 hours, gabapentin will be administered two times a day during waking hours and the dose will not exceed the amount of a topical agent used on average to treat the entire scalp in everyday clinical practice (60 ml per month).

Subjects may directly benefit from analysis of nerve function, CGRP neuropeptide, and treatment with gabapentin, resulting in improvement of their symptoms that may prevent further hair loss and even possible hair growth. This analysis will also help us better understand the disease process in scarring alopecia to further improve management of the condition.

## **2 Study Objectives**

Primary Objective: To assess the role of neurogenic inflammation associated with CGRP expression in scarring alopecia

Secondary Objective: To assess the safety and efficacy of topical 6% gabapentin in subjects with symptomatic scarring alopecia.

## **3 Study Design**

### **3.1 General Design**

This is a cohort study.

Every subject is expected to schedule 6 visits total to complete the study. The total duration of the study for each volunteer is expected to be approximately 14 weeks.

Prior to gabapentin treatment, there is one visit to screen individuals for participation in the study and to obtain consent. After consent is signed, this visit will also include obtaining history from the subject, clinical evaluation, survey completion, neurometer study, photography, and scalp biopsies. At this initial visit, a total of four 4-mm skin biopsies will be collected. Two biopsies will be collected from affected, symptomatic scalp, and two skin biopsies will be collected from clinically unaffected scalp. Routine histology, confocal microscopy examination, and, if indicated, ELISA CGRP level analysis will be performed on the biopsy specimens. Subjects will start topical 6% gabapentin treatment on Visit 2 (Day 0). Four remaining visits will be scheduled to follow subjects after the start of topical 6% gabapentin treatment. Visits 3, 4 and 5 will occur 4, 8 and 12 weeks respectively after treatment with gabapentin is started. These visits will include labwork to check gabapentin blood levels. During Visit 5, the subject will also be reassessed through clinical evaluation, completion of surveys, neurometer study, photography, and four 4-mm scalp biopsies. Visit 6 will be a follow-up visit two weeks after completion of treatment for suture removal and clinical evaluation of the subject.

CONFIDENTIAL

**TABLE 1. Schedule of Study Procedures**

Schedule of Study Procedures	Visit 1 Screening/ Baseline	Visit 2	Visit 3	Visit 4	Visit 5	Visit 6 Follow-up
	Day -14	Day 0	Week 4	Week 8	Week 12	Week 14
Approximate visit duration	2-4 hours	30 min	30 min	30 min	1-2 hours	20 min
Assess inclusion/exclusion criteria, obtain informed consent	X					
Obtain medical history						
Physical examination of scalp	X				X	
Review changes in medical history and medications						
Surveys a	X		X	X	X	
Neurometer study b	X				X	
Record adverse experiences			X	X	X	X
LPPAI clinical assessment c	X	X	X	X	X	
Gabapentin blood level			X	X	X	
Skin biopsies	X				X	
Biopsy suture removal		X				X
Photographs d	X				X	
Topical gabapentin 6% solution BID to affected area		X	X	X		

aSurveys include the Dermatology Life Quality Index (DLQI), Short Form (36) Health Survey (SF-36), Pain Visual Analog Scale (VAS) and Itch Visual Analog Scale (VAS).

bNeurometer study will be performed on three areas: the index finger; normal-appearing, unaffected scalp; affected symptomatic scalp.

cLichen Planopilaris Activity Index (LPPAI) clinical assessment was developed by *Chiang et al.* and published in *JAAD* in January 2010^24.

dPhotographs will focus on the affected symptomatic areas of the scalp at Visit 1. Photographs of the same areas will be taken at Visit 5.

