#### **Treatment Regimen**

Qualified subjects will be educated by the research coordinator on how to properly apply the gabapentin 6% solution two times daily onto intact skin of affected symptomatic scalp areas. The minimum and the maximum size of the scalp areas to be treated will be determined for each subject respectively, based on their disease pattern assessed during Visit 2. Treated sites will be initially recorded and should be treated for the entire 12 weeks unless the skin is adversely affected by the topical gabapentin.

CONFIDENTIAL

This material is the property of the University of Minnesota. Do not disclose or use except as authorized in writing by the study sponsor

Subjects may continue their normal grooming regimen as long as substances without other neuromodulatory agents or steroids are used during the treatment period. Recommended application will be in morning and evening at bedtime. The solution should be applied after hair washing if this coincides with time for application.

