## **6 Study Procedures**

### **6.1 Visit 1 (Screening/baseline)**

Before any study-related procedures are performed, subjects will be screened for participation in the study using inclusion and exclusion criteria. Once determined to be a qualified candidate for participation, subjects will be asked to read and sign the consent form if they wish to participate in this research study. They will then be asked about their medical and medication history.

The following tests and procedures will be performed:

- Obtain medical history and medications
- Physical examination of scalp
- Lichen Planopilaris Activity Index (LPPAI) clinical assessment will be performed. Every effort will be made to have the same person evaluate the alopecia at each visit for any given subject.

CONFIDENTIAL

- Scalp photography, especially affected areas that will be monitored and treated with gabapentin
- Subject to complete surveys to assess symptomatology pre-treatment: DLQI, SF-36, Pain VAS and Itch VAS
- Neurometer study to assess A $\beta$ , A $\delta$ , and C fiber function before gabapentin administration
- Collect four pre-treatment skin biopsy samples: two 4-mm biopsy specimens from affected scalp and two 4-mm biopsy specimens from normal-appearing scalp. Specimens will be analyzed for routine histology, confocal microscopic examination, and CGRP level.

If potential symptomatic subjects are currently taking medications/treatments for their scarring alopecia, they will be asked to stop the treatment as noted in the exclusion criteria in section 4.2.

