#### **6.5 Visit 5 (Week 12)**

The following tests and procedures will be performed:

- Record adverse experiences
- Physical examination of scalp
- Gabapentin blood level
- Review changes in medical history and medications since Visit 4
- LPPAI clinical assessment
- Scalp photography, especially affected areas that are being monitored and treated with gabapentin
- Subject to complete surveys to assess symptomatology: DLQI, SF-36, Pain VAS and Itch VAS
- Neurometer study to assess A $\beta$ , A $\delta$ , and C fiber function after gabapentin administration
- Collect and assess third container of gabapentin solution
- Collect four post-treatment skin biopsy samples: two 4-mm skin biopsy specimens from affected scalp and two 4-mm biopsy specimens from normal-appearing scalp. Specimens will be analyzed for routine histology, confocal microscopic examination, and CGRP level.

Subject has now completed the entire twelve weeks of topical gabapentin therapy.

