## 7 Statistical Plan

### 7.1 *Sample Size Determination*

This is a pilot study with the plan to enroll 10 subjects. The reasoning for sample size selection is to proceed with preliminary studies in a small group. All subjects will be selected based on inclusion and exclusion criteria.

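### Visit 5 biopsy and neurometer sites are not tied to the Visit 1 sites or to the treated area, and the neurometer rule, read literally, asks for scalp that is still symptomatic at Week 12

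*Protocol*

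**What the plan says.** **Baseline.** At Visit 1 (Day -14), section 3.1 states: "Two biopsies will be collected from affected, symptomatic scalp, and two skin biopsies will be collected from clinically unaffected scalp". Section 6.1 gives the same split without the word *symptomatic*: "Collect four pre-treatment skin biopsy samples: two 4-mm biopsy specimens from affected scalp and two 4-mm biopsy specimens from normal-appearing scalp". Neither asks for the sampled points to be recorded.

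**Week 12.** Section 6.5 asks for "two 4-mm skin biopsy specimens from affected scalp and two 4-mm biopsy specimens from normal-appearing scalp". It refers neither to the Visit 1 sites nor to the treated area.

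**Neurometer.** One footnote to Table 1 (footnote b) covers Visits 1 and 5: "Neurometer study will be performed on three areas: the index finger; normal-appearing, unaffected scalp; affected symptomatic scalp".

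**Photographs.** Footnote d does fix the location: "Photographs of the same areas will be taken at Visit 5".

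**Treated area.** The Treatment Regimen text in section 5.1 sets the area for each subject "based on their disease pattern assessed during Visit 2", that is, on Day 0. The treated sites are then recorded and kept for the 12 weeks unless the skin reacts badly.

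**Use of the data.** Section 3.2 uses the Week 12 biopsies to judge the effect of gabapentin on the disease and on CGRP. Sections 5.2 and 5.7 state that there is no control group and no blinding. Section 7.1 states: "This is a pilot study with the plan to enroll 10 subjects".

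**The concern.** With no control group, the within-subject change from Visit 1 to Visit 5 is the only evidence here of a drug effect on CGRP or nerve function. That change can be interpreted only if both readings come from comparable skin, and the protocol leaves the second location to unblinded staff.

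Two things are at stake. First, a pair taken from different areas mixes differences between areas with change over time. Second, where the rule asks for scalp that is symptomatic at Week 12, eligibility for sampling depends on the outcome: skin that improved drops out and skin that did not improve qualifies. An analysis plan cannot repair either problem, because a location that was never recorded cannot be recovered and a biopsy cannot be retaken.

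**Working it through.** The protocol gives no power, effect size or variance for these measures, so there is no figure to reproduce. The main check is to compare the text on each measure.

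| Measure | Visit 1 site | Visit 5 site | Tied to Visit 1 site? | Tied to treated area? |
|---|---|---|---|---|
| Photographs | affected, symptomatic areas | the same areas | yes | partly (sections 6.1 and 6.5 stress treated areas) |
| Neurometer | affected and symptomatic; normal-appearing; finger | identical wording | no | no |
| Biopsies | affected (section 3.1 adds symptomatic); normal-appearing | affected; normal-appearing | no | no |

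**Neurometer.** Footnote b applies the same description at both visits. Taken literally, a Visit 1 site that is symptom-free at Week 12 no longer fits. The operator must then use another area that is still symptomatic, or has none to use.

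**Biopsies.** *Symptomatic* does not appear at Visit 5. Section 1.1 describes the hair loss as permanent, so scalp can remain affected after its symptoms settle. The affected sample can come from a different area, but the wording does not push it towards skin that failed to respond.

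**Untreated skin.** The treated area is set 14 days after baseline sampling. A Visit 5 point could lie outside it through spread after Day 0 (spreading is a scored LPPAI item), or because an area was left out at Visit 2. A site taken off treatment for a skin reaction would also still count as affected.

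**Comparator.** The normal-appearing site is likewise chosen afresh at Visit 5.

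**Illustrations.** Only n = 10 comes from the protocol; every other input is an assumption.

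1. *No qualifying neurometer site.* If a proportion p of subjects become symptom-free, independently, P(at least 1 of 10) = 1 - (1 - p)^10.
   - p = 0.1: 1 - 0.9^10 = 65%
   - p = 0.3: 1 - 0.7^10 = 97%
   - p = 0.5: 1 - 0.5^10 = 99.9%

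2. *Selecting the least-improved site (worst case for the neurometer).* Let the true mean change be -0.50 SD, with site-to-site spread t and K candidate sites. A fixed site returns -0.50. The least-improved site returns -0.50 + t × e(K), where e(K), the expected largest of K standard normal values, is 0.564, 0.846 and 1.163 for K = 2, 3 and 5.
   - t = 0.25: -0.36, -0.29, -0.21
   - t = 0.5: -0.22, -0.08, +0.08

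3. *Unmatched sites without selection.* The standard error of the mean change is SD × √(2(1 - r)/10), where r is the correlation between the two visits.
   - r = 0.8: √(0.4/10) = 0.20 SD
   - r = 0.4: √(1.2/10) = 0.35 SD
   - r = 0: √(2/10) = 0.45 SD

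   Mismatched locations would be expected to lower r, so precision is lost even where no bias arises.

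**The case against.** The strongest reply is that no sentence says the Week 12 site is chosen by its state at Week 12. Footnote b is one list of regions for two visits, and its wording resembles footnote d, which is anchored to Visit 1. A sensible operator may read it as the area so designated at baseline. That reading is available, but the text does not require it, and the authors wrote a same-area rule for photographs and none for these measures. The ambiguity stands.

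A reader might infer that the CGRP change is also systematically drawn from non-responding skin. The documents do not support that: section 6.5 says only affected scalp, and permanent hair loss leaves responders with scalp that qualifies. A reader might also infer that untreated skin will commonly be sampled. That too goes too far: drug is applied to affected, symptomatic areas, the treated sites are recorded and held, Visits 1 and 2 are two weeks apart, and the Visit 1 photographs already cover areas to be treated.

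Three further points stand in full. The comparison of affected with unaffected scalp at Visit 1, which also serves the primary objective, is untouched. The net direction of any bias is unproven: subjects enter with symptoms and there is no control, so regression to the mean would push towards apparent improvement. And section 7.2 plans descriptive statistics, with symptom and sign scores compared with baseline; no test or decision rule rests on the paired CGRP or neurometer change.

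**Conclusion.** The gap is real and follows from the text alone: Visit 5 biopsies and neurometer readings need not come from the Visit 1 location or from recorded treated skin. For the neurometer, the literal wording makes the site depend on the outcome and leaves a symptom-free responder without a defined reading. For the biopsies, the before/after CGRP comparison can involve different areas; selection towards non-responding skin, and sampling of untreated skin, are possibilities rather than consequences of the wording.

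The size of any bias cannot be derived from the protocol. The shift from -0.50 SD to between -0.36 and +0.08 SD assumes that the least-improved of two to five sites is always chosen and that the between-site spread is 0.25 to 0.5 SD. It shows what an open site rule could do and is not a forecast. In a 10-subject descriptive pilot this is a moderate point. It should be settled before the first Visit 1 biopsy, because it cannot be put right afterwards.

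**What to change.** 1. Section 6.1: mark the Visit 1 biopsy and neurometer points, affected and normal-appearing, on the photographs already taken.
2. Section 6.5 and footnote b: state that Visit 5 samples and readings are taken adjacent to those recorded points, outside the biopsy scars, whether or not the area is still symptomatic.
3. Record for each affected point whether it lies inside the treated area recorded at Visit 2, and flag or report separately the pairs that do not.

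The change concerns only where measurements are taken. It places no condition on where the drug is applied. The cost is slightly more record-keeping, with no additional visit, biopsy or reader.
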